## **2.4 Eligibility/screening of subjects**

Once participants are contacted by study coordinators, a brief screening questionnaire will be administered over the phone (see attached). Participants who agree to participate will be scheduled for the pre-treatment assessment session where the KBIT-2 and other study measures will be implemented. Final eligibility will be determined after this session.

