## 4.0 Study Design and Procedures

### 4.1 Study Design

Randomized clinical trial with two active conditions and no placebo or waitlist conditions.

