
**(9) Stress experienced in session** will be assessed via ECG. Children will be connected to a UFI 3991/4 EIRS BioLog ambulatory physiological data recorder using disposable Ag/AgCl electrodes prior to the start of treatment sessions 1, 4, 6, 8, and 12. Placement of electrodes will be performed by a research assistant using the procedures specified previously. Event marks will be recorded at the point of transition from the 10-minute

relaxation/pleasurable activities time to the start of the implementation of techniques. RSA will be sampled in 30 second epochs and calculated for each of these two time periods (10 minute phase prior to technique implementation, 45 minute phase of technique implementation). This methodology will allow for assessment of within-participant RSA trajectories over the course of treatment, and between-group comparisons on physiological stress response both prior to and during technique implementation. **(10) Quality of therapeutic rapport** will be assessed via child and caregiver-report using the appropriate versions of the Therapeutic Alliance Scale for Children-Revised (TASC-R; Accurso et al., 2013; Creed & Kendall, 2005; Shirk & Saiz, 1992). AAT is believed to facilitate the development of rapport and, therefore, assessing rapport at multiple points in the first phase of treatment is appropriate. As such, rapport will be assessed at the 2nd and 4th treatment sessions as well as at post-treatment. A research assistant will administer the TASC-R with caregivers and children during these sessions and will explicitly state that the clinician will not be made aware of the answers provided. **(11) Attitudes toward pets** will be assessed for the youth at the pre-treatment assessment only using the Pet Attitude Scale to determine whether pre-existing attitudes toward pets is related to outcome in the TF-CBT+AAT group. **(12) The demographics** form will be completed at the pre-treatment assessment only.

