#### **5.2 Sample size determination**

Although a primary objective of this study is to derive effect size estimates that can inform the design of a larger clinical trial, a preliminary power analysis was conducted. Results indicated that the proposed sample of 60 participants (equal sample sizes across the two conditions) can achieve 80% power to detect an approximately 5 point difference of pre-post change between the groups on the PTS measure (i.e., UCLA) when the standard deviation of each group is assumed to be 6.5 and the significance level is set at .05. Ethnic and gender composition will likely reflect those of the larger Harrisburg area (45% White, 45% African-American, 10% other ethnicities; 50% female, 50% male).

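### The pet-attitude question is framed for the TF-CBT+AAT arm alone, which cannot separate a dog-specific modifier from a general prognostic factor; an exploratory attitude-by-arm interaction would use data already collected

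*Combined protocol and SAP*

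**What the plan says.** Item (11) of Measures, within section 4.2, states that attitudes toward pets "will be assessed for the youth at the pre-treatment assessment only using the Pet Attitude Scale" and gives the reason: "to determine whether pre-existing attitudes toward pets is related to outcome in the TF-CBT+AAT group". This is the only statement of how the scale will be used.

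The Statistical methods section (the second of two sections numbered 5.2) plans a multilevel model comparing outcome trajectories between the arms. Its example adjustment variables are gender, age and number of trauma types. It does not mention the Pet Attitude Scale, any moderator of the treatment effect, or an attitude-by-arm term.

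Three points bear on whether scores will exist in both arms:

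- Item (11) restricts the measurement by time but not by arm.
- Section 2.4 places the study measures in the pre-treatment session and adds: "Final eligibility will be determined after this session".
- Section 4.2 intends the research assistant who conducts assessments to be blind to condition.

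Section 4.1 describes the trial as a "Randomized clinical trial with two active conditions and no placebo or waitlist conditions", so there is a concurrent comparison arm receiving the same therapy without the dog.

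**The concern.** The natural reason to ask about pet attitudes in a trial of therapy dogs is to learn whether the dog helps some children more than others. That is effect modification: a difference between the arms in the slope of outcome on attitude. A slope estimated in the dog arm alone does not measure that difference. If children with warmer attitudes to pets improve more in any trauma-focused therapy, the dog-arm slope looks just as it would if the dog were responsible.

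Entering attitude as one more covariate in the planned model would not help, because a main effect adjusts for attitude without comparing its slope between arms.

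What is at stake is the interpretation of one exploratory result. Section 5.2 (Sample size determination) says a primary objective is to obtain effect size estimates that inform a larger trial, so it is worth having an estimate that can be interpreted.

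**Working it through.** **1. The plan's own figure.** Section 5.2 (Sample size determination) says that "the proposed sample of 60 participants (equal sample sizes across the two conditions" (so 30 per arm) "can achieve 80% power to detect an approximately 5 point difference of pre-post change between the groups", where "the standard deviation of each group is assumed to be 6.5" and "the significance level is set at .05". Sidedness is not stated; I assume two-sided.

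Detectable difference at 80% power = (1.960 + 0.842) × 6.5 × √(2/30) = 4.70 points by the normal approximation, or 4.78 with the t distribution. At exactly 5 points, power is 84.6% (normal) or 83.4% (t). The stated figure reproduces within its rounding. It concerns the main between-arm contrast and is unaffected by what follows.

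**2. Set-up for the attitude question.** These assumptions are mine, not the documents': 

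- attitude is standardised, with the same spread in both arms;
- each child has one change score, with SD 6.5 in the arm where attitude matters;
- the attitude-outcome correlation r runs from 0.2 to 0.5;
- the residual SD is the same in both arms;
- there is no dropout and no clustering by dog.

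Slope = 6.5r points per SD of attitude. Residual SD s = 6.5√(1 − r²).

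Two situations are compared. In the *purely prognostic* one the slope is the same in both arms. In the *dog-specific* one the slope exists only in the TF-CBT+AAT arm.

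**3. Formulas.**

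- AAT-only slope: standard error s/√29, 28 df, noncentrality r√29/√(1 − r²).
- Attitude-by-arm interaction, all 60 youth: standard error s√(2/29), 56 df. When the effect is dog-specific, noncentrality is r√(29/2)/√(1 − r²).

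The SD of 6.5 cancels, so for a given r the rejection rates do not depend on it. The interaction's standard error is √2 = 1.41 times that of the one-arm slope.

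Example at r = 0.3: s = 6.5 × √0.91 = 6.20. AAT-only noncentrality is 1.95/(6.20/√29) = 1.69, giving power 37.3%. Interaction noncentrality is 1.69/1.41 = 1.20, giving power 21.8%.

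**4. Simulation, 20,000 trials per situation.** Monte Carlo standard error is at most √(0.25/20,000) = 0.35 percentage points.

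| r | Slope | AAT-only, purely prognostic | AAT-only, dog-specific | Interaction, purely prognostic | Interaction, dog-specific (formula) |
|---|---|---|---|---|---|
| 0.2 | 1.30 | 18.4% | 18.5% | 4.9% | 12.0% (11.9%) |
| 0.3 | 1.95 | 36.7% | 37.1% | 5.1% | 21.4% (21.8%) |
| 0.4 | 2.60 | 60.7% | 60.4% | 5.1% | 35.9% (37.2%) |
| 0.5 | 3.25 | 82.7% | 82.4% | 5.0% | 55.7% (58.0%) |

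With r = 0 both tests reject in about 5% of trials. The formula for the AAT-only test gives 18.6%, 37.3%, 62.1% and 85.1%. It runs slightly high because it fixes the sum of squares of attitude at 29, whereas the simulation lets it vary.

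**5. Reading.** The two AAT-only columns agree within simulation error at every r, so that test carries no information about which situation holds. The two interaction columns differ, but not by much at small r.

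**6. Precision.** With residual SD 6.5, the slope detectable with 80% power is about 3.5 points per SD of attitude in one arm, and about 4.9 for the difference between arms.

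**The case against.** The strongest reply is that item (11) asks only whether attitude is related to outcome in one group, and a within-group association answers that question. Taken literally this is right. In the simulation attitude really is related to outcome in that group, so the 18% to 83% are correct detections. A reader might take them as inflated type I error when they are set beside the interaction's 5%. They are not: the two tests address different null hypotheses. What survives is that the literal question has little use unless one also asks whether the dog is responsible, and the one-arm answer does not bear on that.

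Three other inferences go further than the documents:

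- *That a one-arm test is planned.* Item (11) states an aim, and no test is specified anywhere.
- *That the sponsor will conclude dogs work better for children who like pets.* No passage claims moderation.
- *That the larger trial would select or stratify on pet attitude.* No passage proposes this.

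It is also fair to say that the interaction is weak at this sample size. Its power stays below 60% even at r = 0.5. Dropout and clustering by the three dogs would lower it, and the exclusion of children with fear of dogs, dog allergy or aggression toward animals (section 1.2) may narrow the range of attitudes and lower it further. This limits the gain. It does not favour the one-arm slope, whose higher rejection rate is the same whether or not there is any modification.

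**Conclusion.** The point holds as a minor, exploratory improvement. The stated aim is confined to one arm, no analysis is specified, and the control-arm scores that would make the result interpretable should already be available.

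Under the assumptions listed, an AAT-only test is significant about equally often whether attitude is purely prognostic or dog-specific (about 37% in both cases at r = 0.3). The interaction stays near 5% in the purely prognostic case and has power of about 12%, 22%, 37% and 57% for a dog-specific effect at r = 0.2, 0.3, 0.4 and 0.5.

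That the one-arm analysis does not discriminate follows from the design and does not depend on the value of r; only the percentages do. They also rest on a single change score per child, so precision in the planned trajectory model will differ.

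**What to change.** Reword item (11) so that the aim is to examine whether the difference between arms in outcome varies with pre-treatment attitude toward pets.

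Add to Statistical methods an analysis labelled exploratory: in the planned multilevel model for posttraumatic stress (UCLA), include attitude × arm × time with all its lower-order terms, keeping the planned nesting by dog. The choice of the UCLA is mine, since item (11) says only outcome; the sponsor should name the outcome it wants.

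Report the attitude slope in each arm, and their difference with a confidence interval. This still delivers the TF-CBT+AAT slope that item (11) asks for. State in advance that a non-significant interaction is not evidence of no modification.

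The cost is one reworded clause, a short addition to the statistical section and a few model terms, with no new data or visits. The downside is a wide interval for the slope difference at N = 60.

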#### **4.3 Duration of Participation**

Each child is expected to participate in the pre-treatment assessment, 12 sessions of treatment, and a post-treatment assessment.

## **Statistical Plan**

#### **5.1 Number of Subjects**

60 participant youth

#### **5.2 Sample size determination**

Although a primary objective of this study is to derive effect size estimates that can inform the design of a larger clinical trial, a preliminary power analysis was conducted. Results indicated that the proposed sample of 60 participants (equal sample sizes across the two conditions) can achieve 80% power to detect an approximately 5 point difference of pre-post change between the groups on the PTS measure (i.e., UCLA) when the standard deviation of each group is assumed to be 6.5 and the significance level is set at .05. Ethnic and gender composition will likely reflect those of the larger Harrisburg area (45% White, 45% African-American, 10% other ethnicities; 50% female, 50% male).

## 5.2 Statistical methods

Intent-to-treat analyses will be used for all statistical analyses (i.e., all of the available data from randomized participants are utilized for analyses). Descriptive statistics (e.g., means, ranges, standard deviations) will be computed for continuous variables; frequencies will be calculated for

categorical variables. Measurements of PTS, emotional and behavioral concerns, and emotion regulation are continuous variables and will be examined over time with individual-level graphical checks. Transformation methods may be needed based on normality checks (i.e., Shapiro-Wilks test). To adjust for potential confounding variables that may be identified (e.g., gender, age, number of trauma types endorsed on the UCLA), multilevel models with partial nesting (i.e., youth in the TF-CBT+AAT group nested by dog, youth in the TF-CBT group not nested) will be employed to investigate the temporal trend and compare the trajectories of outcomes between the two groups using SAS PROC NL MIXED v. 9.4. Note that parameter estimates will be obtained using maximum likelihood estimation, and that p-values can be computed based on Chi-square tests (Liang & Zeger, 1986). If missing data or dropouts occur, the mechanism (i.e., missing completely at random, missing at random) will be explored and adjusted for valid statistical inference.

Analyses of categorical data (i.e., participant attrition, cancelled appointments, missed appointments without prior notice, and ability to implement TF-CBT techniques) will likely utilize descriptive and non-parametric methods (e.g., Fisher's exact tests). Differences between the conditions for treatment satisfaction will be examined with parametric (e.g., between groups t-tests) or non-parametric

analyses (Wilcoxon rank-sum tests). Given the small sample sizes and primary interest in a covariate effect, generalized estimating equations (GEE) can be used for the analysis of repeated cortisol assessments (Wang & Long, 2011). The GEE model with autoregressive (AR) working correlation structure can be fitted to investigate the difference of within session samples and between the treatment and control day samples. Three variables of interest are included: day of sample (0 = control; 1 = treatment), the session status (0 = pre-session; 1 = post-session; 2 = 20 minutes post-session), and their interaction.

Modified variance estimators are calculated to reduce bias when sample sizes are small and t-tests are used for valid inference. The analysis will be conducted using the function of “geesmv” in R (Wang et al. 2016). Similar methods can be used for the analysis of canine heart rate variability and behavior.

With regards to the ECG data, interrupted time series analyses can be used to analyze RSA from two time periods. The covariates of interest include time (in minutes) since the start of RSA assessment, the treatment group (0 = TF-CBT; 1 = TF-CBT+AAT), the time period (0 = phase prior to

technique implementation; 1 = technique implementation), time (in minutes) since technique implementation, and the interactions of the last variables with the treatment group. The correlation among time series observations is represented in the error term. Residual plots can be used to detect the autocorrelation, where the Durbin–Watson statistic can be used. This model can be fitted by SAS PROC AUTOREG v. 9.4. Regression-based mediational analyses can be conducted at each of the four assessment sessions to examine if therapeutic rapport mediates the relationship between the presence of the dogs and PTS outcomes. Bootstrap or Monte Carlo methods can be applied to testing significance of the indirect effect (Tofighi & MacKinnon, 2015). This model can be fitted using the PROCESS macro for SAS v. 9.4 (Hayes, 2013).

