**(3) Emotion regulation** will be assessed in three ways. First, caregivers will complete the Emotion Regulation Checklist (ERC; Shields & Cicchetti, 1997) during the pre- and post-treatment assessments. Similarly, children will complete the self-report Emotion Regulation Index for Children and Adolescents (ERICA; MacDermott et al., 2010) during the pre- and post-assessments. Last, children's resting and stress reactivity respiratory sinus arrhythmia (RSA) will be assessed both pre- and post-treatment. RSA is assessed via an electrocardiogram (ECG) and is a well-established psychophysiological marker of emotion regulation (Beauchaine, 2015). RSA will be assessed with a UFI 3991/4 EIRS BioLog ambulatory physiological data recorder using disposable Ag/AgCl electrodes. Electrodes will be placed on the chest and abdomen to acquire inter-beat intervals. Placement of the electrodes will be facilitated by the research assistant conducting the assessment and the child's caregiver will be present during the application and later removal of the electrodes. The caregiver will not be present during the administration of the assessment procedures. To assess resting RSA, children will watch pre-selected television programs that are not emotionally-laden for 15 minutes. Stress reactivity will then be assessed using the Trier Social Stress Test (TSST; Buske-Kirschbaum et al., 1997; Kirschbaum et al., 1993). In addition, children will be shown a \$15 gift card to a toy or electronics store prior to beginning the TSST and told that they must achieve a satisfactory performance across the TSST tasks to earn the gift card. The gift card will be provided to all participants at the completion of the TSST. In both the resting and stressor paradigms, RSA will be sampled in 30 second epochs. [name], who will be blind to participant condition, will be responsible for editing the ECG files to remove artifacts and scoring the files using CardioEdit and CardioBatch software (Brain-Body Center, University of Illinois at Chicago, 2007). [name] is trained and certified by the developers in the use of this software. **(4) Youth perception of the caregiver** will be assessed at both the pre-treatment and post-treatment assessment sessions using the Security Scale, to determine whether participation in TF-CBT improved the youth's perception of their caregiver as a source of support. To examine potential caregiver-

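### Emotion-regulation outcomes have two measurements but are given only a trajectory model; a baseline-adjusted contrast should replace it, and within-arm change on the stress test should not be interpreted

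*Combined protocol and SAP*

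**What the plan says.** **Timing.** Section 4.2, Measures, item (3), lists three kinds of emotion-regulation measure. The caregiver-reported ERC is completed "during the pre- and post-treatment assessments" and the child-reported ERICA "during the pre- and post-assessments". For the physiological measure, "children's resting and stress reactivity respiratory sinus arrhythmia (RSA) will be assessed both pre- and post-treatment". Each therefore has two waves. By contrast, items (1) and (2) place the UCLA and the SDQ at four points (pre-treatment, sessions 5 and 9, post-treatment), and the protocol rests its comparison of rates of progress on the four UCLA points.

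**Analysis.** Section 5.2, Statistical methods, states: "Measurements of PTS, emotional and behavioral concerns, and emotion regulation are continuous variables and will be examined over time"; the sentence ends by naming graphical checks for each individual. It then names one multilevel model, with youth in the dog arm nested by dog, which "will be employed to investigate the temporal trend and compare the trajectories of outcomes between the two groups". No separate form is given for outcomes with two waves. The interrupted time series later in that section concerns RSA recorded during treatment sessions (item 9), not the pre- and post-treatment assessments.

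**Stress test.** Under item (3), children are told before the TSST that the gift card depends on satisfactory performance. Then: "The gift card will be provided to all participants at the completion of the TSST". Reactivity is assessed at both visits, so the procedure is repeated. Section 4.1 describes two active arms with no waitlist or placebo.

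**The concern.** A comparison of trajectories suits the four-wave outcomes. Applied to two waves it can deliver only a difference in mean change, and the plan does not say so or choose the form of that comparison. The more precise use of the baseline already collected is left out. This matters because there are only 60 youth, and because section 5.2, Sample size determination, makes effect-size estimates for a larger trial a primary objective.

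The stated interest in a temporal trend also invites a reading of within-arm change. For TSST reactivity, a fall from the first to the second test could reflect treatment, familiarity with the test, or a changed response to the incentive. Nothing in the design separates these within an arm.

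**Working it through.** **Inputs.** Two waves for ERC, ERICA, resting RSA and TSST RSA; four for UCLA and SDQ (section 4.2, Measures). 60 youth, equal arms, so 30 per arm (sections 5.1 and 5.2). The pre-post correlation r is not given; 0.3, 0.5 and 0.7 are assumed.

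**The plan's own figure.** Section 5.2 gives a detectable difference of about 5 points in UCLA change, with SD 6.5 and 80% power. Taking alpha .05 as two-sided and 6.5 as the SD of change: (1.960 + 0.842) × 6.5 × √(2/30) = 4.70 points, or 4.78 with the t distribution. This agrees with the plan. It concerns the UCLA only and is unaffected by this point.

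**What two waves can estimate.**
- *Means.* Intercept, arm, time and arm-by-time are 4 columns of rank 4, so all are estimable. Adding a quadratic in each arm gives 6 columns but still rank 4 at two waves; at four waves the rank is 6. Trajectory shape is therefore out of reach with two waves.
- *Covariance.* With times 0 and 1, a random intercept (variance a), random slope (variance b), their covariance c and residual variance e imply var(pre) = a + e, var(post) = a + 2c + b + e, and cov = a + c. That is four parameters against three moments (rank 3), so they are not identified. At four waves there are ten moments and the rank is 4. A random intercept plus residual alone is identified at two waves (rank 2 of 2).
- *Arm-by-time term.* In simulated two-wave trials with complete data and a random intercept, it equalled the between-arm difference in mean pre-post change to within 2e-14.

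**Precision.** Let both waves have variance s².
- Change score: variance per child 2s²(1 − r).
- Post-treatment value adjusted for baseline: s²(1 − r²).
- Ratio: (1 − r²) / [2(1 − r)] = (1 + r)/2.

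| Assumed r | Change score (× s²) | Baseline-adjusted (× s²) | Ratio | Youth needed by change score to match 60 adjusted |
|---|---|---|---|---|
| 0.3 | 1.40 | 0.91 | 0.65 | 60/0.65 ≈ 92 |
| 0.5 | 1.00 | 0.75 | 0.75 | 60/0.75 = 80 |
| 0.7 | 0.60 | 0.51 | 0.85 | 60/0.85 ≈ 71 |

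The direction does not depend on equal variances. With SDs s0 (pre) and s1 (post), the change-score variance minus the adjusted variance is s0² + s1² − 2r·s0·s1 − s1²(1 − r²) = (s0 − r·s1)², which is never negative.

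**Repeated stress test.** 400 two-wave trials were simulated with 30 per arm and a true arm effect of 0.70. The mean arm-by-time estimate was 0.72 with no shift at the second test, and 0.73 with a shift of −3 common to both arms. The SD of the estimates was about 0.35, so the simulation error of each mean is about 0.35/√400 ≈ 0.02. A shift shared by both arms leaves the between-arm contrast unbiased, but it enters the within-arm change in full.

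**The case against.** Several objections have force.

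- **The plan only implies that these outcomes enter the model.** The sentence grouping them ends with graphical checks, and the modelling sentence says only outcomes. This is correct. But no other analysis is named for them, so either they enter the trajectory model or they have no specified analysis. Both need the same correction.
- **A reader might infer that the comparison cannot be estimated or interpreted, or that the model will fail.** The documents do not support this. The arm-by-time contrast is estimable and is an ordinary treatment contrast. Section 5.2 specifies no child-level random slope; the only nesting it names is by dog.
- **A reader might infer that a change score is the least precise choice.** It is not. A post-only comparison has variance s², which exceeds 2s²(1 − r) whenever r > 0.5. A likelihood model with a common baseline mean would already recover essentially the adjusted precision; the plan does not say whether the baseline means are constrained. The issue is thus efficiency and specification, not invalidity.
- **A reader might infer that at the second test children know the card is unconditional.** The documents describe no debriefing. A child told to perform well who then receives the card may conclude that the performance was satisfactory. The text shows only that the card has been received once.
- **A reader might infer that the repeated incentive biases the trial's comparison.** Any such effect concerns TSST reactivity alone: ERC and ERICA are questionnaires, and resting RSA is recorded before the stressor. It is by design common to both arms, and would bias their contrast only if it, or attrition, differed by arm.

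**Conclusion.** The point holds as one of specification and efficiency. For ERC, ERICA, resting RSA and TSST reactivity, the named model can yield no more than a difference in mean change. That contrast is valid, but baseline adjustment would remove about 15% to 35% of its variance for r between 0.7 and 0.3. The size rests on an assumed r, equal variances at the two waves, complete data, and no allowance for clustering by dog.

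Within-arm change in TSST reactivity cannot be attributed to treatment, because the test and incentive are repeated and there is no untreated arm. The size of any repeat-test or incentive effect cannot be derived from the documents. The between-arm TSST contrast stands, as do the UCLA analysis and its sample-size figure.

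**What to change.** In section 5.2, Statistical methods, separate the two-wave outcomes from the trajectory model and state the following.

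1. For ERC, ERICA, resting RSA and TSST reactivity, the estimate is the post-treatment arm difference adjusted for the outcome's own pre-treatment value, with the dog term kept.
2. Preferably, fit this as a two-wave likelihood model with a common baseline mean in the two arms. A complete-case regression on the post-treatment value would drop youth without that assessment, against the section's own rule of using all available data from randomized participants.
3. Define TSST reactivity within each visit, and adjust for pre-treatment reactivity (and pre-treatment resting RSA if wanted). Do not adjust for post-treatment resting RSA: it is measured after randomization and is itself an outcome, so conditioning on it changes the quantity estimated and can bias the arm effect.
4. For TSST reactivity, report only the between-arm difference, and do not interpret within-arm change as a treatment effect.

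The cost is a short change of wording and a simpler model, made before these outcomes are analysed by arm. No new data are needed.

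### The in-session RSA model does not adjust for the pre-treatment resting RSA already collected, so the between-arm level contrasts lose precision

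*Combined protocol and SAP*

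**What the plan says.** The model for in-session RSA is in section 5.2 Statistical methods, in the paragraph on ECG data. It states: "The covariates of interest include time (in minutes) since the start of RSA assessment, the treatment group". It then adds an indicator for the phase (before or during techniques), time since techniques began, "and the interactions of the last variables with the treatment group". I read that last phrase as group by phase and group by time since techniques began. The list has no baseline RSA.

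The adjustment for gender, age and number of trauma types, earlier in the same section, belongs to the multilevel models for PTS, emotional and behavioral concerns, and emotion regulation. It does not mention baseline RSA either.

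Item (9) of Measures gives the aim of the in-session recordings as within-child trajectories and "between-group comparisons on physiological stress response both prior to and during technique implementation". Item (3) of Measures provides a resting value before and after treatment: "To assess resting RSA, children will watch pre-selected television programs that are not emotionally-laden for 15 minutes". Items (3) and (9) use the same recorder model and the same 30-second epochs.

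On timing, section 2.4 settles final eligibility only after the pre-treatment session, and section 4.2 describes assignment after describing that session. Together they imply that the resting record precedes assignment. No sentence says so outright.

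**The concern.** RSA level differs from child to child, and the trial enrols ages 6 to 17. A between-arm comparison of raw in-session RSA level therefore carries each child's usual level as well as any response to the session. A measure of that usual level, taken before treatment, is planned for both arms and is not used.

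Nothing recorded in session can take its place. Section 4.2 has the dog in the room with TF-CBT+AAT children during the 10 minutes before techniques, so that phase is already under the assigned condition.

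The level contrasts matter for the same reason. If the dog shifted RSA equally in both phases, the shift would cancel out of the group-by-phase term and show only in the level contrasts. Section 5.2 Sample size determination makes effect size estimates for a larger trial a primary objective, so the precision of these estimates has practical value.

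**Working it through.** **Inputs from the documents.** Total sample: "60 participant youth" (section 5.1). Allocation: "equal sample sizes across the two conditions" (section 5.2 Sample size determination), so 30 per arm. Epochs of 30 seconds give 10 × 2 = 20 before techniques and 45 × 2 = 90 during them.

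**Not in the documents.** The SD of RSA, dropout, and the correlation r between a child's resting RSA and mean in-session RSA. I work in SD units with 60 complete children and take r from 0.3 to 0.7 as an assumption.

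**The plan's own figure.** The only power statement concerns the UCLA: the sample "can achieve 80% power to detect an approximately 5 point difference of pre-post change between the groups" when "the standard deviation of each group is assumed to be 6.5 and the significance level is set at .05". With a two-sided test (assumed; sidedness is not stated):

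- Normal approximation: (1.960 + 0.842) × 6.5 × √(2/30) = 4.70 points.
- t-test: 4.78 points. At exactly 5 points, power is 83.4%.

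Both agree with a difference of about 5 points. In SD units the t-test figure is 4.78/6.5 = 0.736. This is the starting point for any unadjusted level contrast with 30 per arm. No figure is stated for RSA.

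**Gain from adjustment.** For a between-child level contrast, adjusting for a baseline covariate multiplies the variance by (1 − r²) × (1 + 1/(N − 4)). With N = 60 the second factor, the price of estimating the covariate's slope, is 1 + 1/56 = 1.018. The standard error (SE) factor is the square root, the equivalent unadjusted N is 60 divided by the variance factor, and the detectable difference is 0.736 times the SE factor.

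| r (assumed) | Variance factor | SE factor | Equivalent N | Detectable at 80% power (SD) |
|---|---|---|---|---|
| 0 | 1.018 | 1.009 | 58.9 | 0.742 |
| 0.3 | 0.926 | 0.962 | 64.8 | 0.708 |
| 0.5 | 0.763 | 0.874 | 78.6 | 0.643 |
| 0.7 | 0.519 | 0.720 | 115.6 | 0.530 |

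**Check by simulation.** The listed model was fitted to 30 children per arm with 20 + 90 epochs each, in 600 runs per setting. The assumed child effect had SD 1 and the epoch error SD 0.7 with lag-one autocorrelation 0.5. Here the assumed correlation is between resting RSA and the child's stable level. Entries are the ratio of adjusted to unadjusted SE.

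| Correlation | Level before techniques | Level during techniques | Group × phase | Group × time since techniques |
|---|---|---|---|---|
| 0.3 | 0.96 | 0.95 | 1.000 | 1.000 |
| 0.5 | 0.90 | 0.88 | 1.000 | 1.000 |
| 0.7 | 0.79 | 0.76 | 1.000 | 1.000 |

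The direction agrees with the formula and the gains are somewhat smaller. With 600 runs each simulated SE is itself uncertain by about 1/√1200 = 2.9%. The two interactions do not move, because each child contributes the same epochs to both phases and anything constant within a child cancels.

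**The case against.** **Bias.** A reader might infer that the unadjusted comparison is biased, or that chance imbalance is a further harm. It is not. Children are randomised, so the unadjusted level contrasts are unbiased. The SD of the arm difference in mean resting RSA is √(2/30) = 0.258 SD, so under simple randomisation an imbalance above 0.25 SD occurs about 33% of the time. At r = 0.3 to 0.7 it would move the contrast by 0.08 to 0.18 SD (r × 0.25). That movement is already in the unadjusted SE. Section 4.2 also blocks to balance gender and age, so 33% is too high to the extent that these drive RSA.

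**Scope.** A reader might also infer that stable child differences contaminate the whole treatment comparison, including the change when techniques begin. The interactions in the plan contradict this. With balanced epochs they are free of such differences, and the point is confined to the two level contrasts.

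**Size.** The correlation is assumed. One record of a child watching television would serve for play and therapy in weekly sessions as late as session 12, and nothing in the documents supports a high r over that change of setting and time. This objection stands: the gain may be small, and the figures are illustrative.

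**Wording.** The ECG paragraph is permissive, so adjustment is unplanned, not excluded. That too stands. Prespecifying it still has a use, because it removes a later choice between adjusted and unadjusted results.

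**Error structure.** The paragraph names PROC AUTOREG and serial correlation but no child-level term for 60 children with up to five recorded sessions each. The gains above presuppose valid between-child SEs, and one covariate does not supply them. This is correct and is a separate point.

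**Conclusion.** The point holds for the between-arm level contrasts in in-session RSA, before and during techniques. Omitting pre-treatment resting RSA gives up precision in both. With 30 per arm and an assumed r of 0.3 to 0.7, adjustment would multiply the SE by about 0.96 to 0.72. The difference detectable with 80% power would fall from 0.74 SD to between 0.71 and 0.53 SD. If r is near zero, the SE rises by about 1%.

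These figures assume 60 children with usable records, a valid between-child SE, and a resting record that precedes assignment, which the documents imply without stating it.

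The UCLA power statement is unaffected and nothing planned is invalidated. This is a nearly free improvement to one secondary part of the analysis.

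**What to change.** In the ECG paragraph of section 5.2 Statistical methods:

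- Add pre-treatment resting RSA, defined as the mean of the artifact-edited 30-second epochs from the 15-minute rest, as a prespecified fixed covariate in every between-group model of in-session RSA.
- Report the between-arm level contrasts before and during techniques adjusted for it.
- Keep children whose resting record is missing, using mean imputation of the covariate with a missing indicator. This fits the plan's intent-to-treat rule.
- State that the resting record is taken before assignment, if that is the case.

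The cost is a few sentences of analysis wording, with no new data, visit or equipment. The child-level term for repeated epochs and sessions has to be specified separately; this covariate does not stand in for it.
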